### **8.4 Six Month Effectiveness and Clinical Status**

Effectiveness at six months will be descriptively summarized in terms of the number and percentage of subjects achieving stable IA occlusion, measured by Raymond Roy classification I or II without the need for re-treatment of the target IA and good clinical outcome defined by mRS and shift tetrachotomized (0,1, 2, 3-6) analysis. 95% two-sided confidence intervals will be provided to evaluate the statistical precision of the estimates. If these endpoints are available at three months but not at six months, the three month values will be used for these analyses.

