Statistical Analysis	
The rates of all adverse events occurring within 24 hours post procedure, hospital discharge status and after discharge for all opened devices at each participating clinical site during the surveillance period will be summarized. The numbers of individual adverse events of each type and the per subject incidence rate for each type of adverse event will be determined and reported along with 90% two-sided exact binomial confidence intervals. Separate event counts and incidence rates with corresponding confidence intervals will be summarized for adverse events determined to be serious, device-related, serious and device-related, procedure-related, serious and procedure-related, and severe. Listings for all adverse events will be compiled that provide full descriptions of each adverse event including determination of the severity, seriousness, and relationship to the device or procedure. Discharge status will be described with counts and percentages.
 
Effectiveness at six months will be descriptively summarized in terms of the number and percentage of subjects achieving successful aneurysm occlusion measured by Raymond scale grade I and II and by clinical outcome as measured by mRS shift analysis comparing preprocedure mRS (up to 24 h prior to treatment) with 6 month mRS. In addition, tetrachotomized (0,1, 2, 3-6) mRS analysis will also be performed. mRS will also be evaluated at discharge and 30 days. Successful aneurysm occlusion will also be evaluated at the end of procedure. Stability of occlusion will be evaluated by comparing the two angiographic studies that are 6 months apart. The distribution of scores will be summarized by counts and percentages. If only three month Raymond scale value is available but not the six month, the three month value will be used in these analyses. Similarly, the last available earlier mRS values will be used if the six month value is not available.

-----------------------------	--

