### **Efficacy**

- Successful intracranial aneurysm occlusion (measured by Raymond Roy classification I or II) at the end of procedure, using digital subtraction angiography (DSA).
- Successful intracranial aneurysm (IA) occlusion, that is a stable IA occlusion, measured by Raymond Roy classification I or II taken at 6 months ( $\pm 21$ d) post procedure without the need for re-treatment of the target IA, using DSA.
- Good clinical outcome- mRS shift @ 6 months (change @ 6 months from pre procedure) and tetrachotomized (0,1, 2, 3-6) mRS analysis.

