## **7.3 Procedure**

### **7.3.1 Angiography**

Intraprocedural diagnostic catheter angiography will be conducted prior to device deployment to determine location and aneurysm morphological features. Diagnostic angiograms will be obtained as per standard of care. A final post-procedure angiogram (full A-P lateral image) will be obtained once all treatments have concluded, including rescue therapy, if necessary. CT of up to 24h postprocedure if performed as a standard of care will be analyzed for safety parameters, such as hemorrhage.

Angiography at end of procedure and 6 months, will be analyzed to determine Raymonds scale at both time points and stability of Raymond Roy score. All images are to be de-identified and submitted to the core lab for review:

The University of California at Los Angeles with the following address:

Angiography and Noninvasive Imaging Core Lab  
[name], FAAN, FAHA, FANA  
UCLA Department of Neurology  
Neuroscience Research Building  
[name]  
[name]

Procedure will be handled as standard of care, according to Comaneci device IFU, appendix A.

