## 8. STATISTICAL ANALYSIS-

### 8.1 General Principles

The detailed hypothesis generation and statistical method is provided below:

The primary effectiveness endpoint is successful intracranial aneurysm occlusion (measured by Raymond Roy classification I or II) at the end of procedure, using digital subtraction angiography (DSA).

The performance goal (PG) for evaluating effectiveness is based on outcomes as reported in the Comaneci de novo, which was successful aneurysm occlusion of 79.7% (51/64). The PG for the primary effectiveness is defined as success rate cited above minus a margin of 10%, therefore giving a PG of 69.7%.

The resulting null and alternative statistical hypotheses are as follows:

H0:  $p \leq PG$

HA:  $p > PG$

The hypothesis test will be performed at an overall two-sided alpha level of 0.05 using Chi-square test, in which the lower confidence bound on the observed incidence of success is compared to the PG.

With a hypothesized true incidence rate of 82.6% for successful intracranial aneurysm occlusion at the end of procedure and desired power of  $\geq 80\%$ , using a normal approximation test with a nominal 0.025 one-sided significance level (equivalent to a two-sided alpha=0.05), the required evaluable sample size for primary efficacy is 90 evaluable patients with a power of 80%.

The objective of this postmarket surveillance study is to reduce uncertainty regarding the safety profile of the device and its real-world performance. This objective will be met by capturing safety data as the device is used in practice by physicians in the United States. As specified by FDA's order to conduct a postmarket surveillance study under section 522 of the Federal Food, Drug and Cosmetic Act (the act), 21 U.S.C. 360l, a total N=120 deployed devices with complete 30 day post procedure patient status. This number of deployments was later adjusted and approved by the FDA to 90 in the current version of the protocol (version 2.0) as explained above. The focus of the study is to characterize the incidence and nature of periprocedural events occurring within 24 hours post-procedure as well as hospital discharge status and to characterize 30-day post-procedure status including 30-day functional status and all adverse events after discharge to day 30 for each use of the Comaneci Embolization Assist Device. Longer terms effectiveness at six months will be also descriptively summarized in terms of the Raymond scale and mRS.

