### **8.6 Missing Data**

Since the primary safety endpoint is defined immediately post-procedure and up to 30 days, the amount of missing data for this study is anticipated to be low and so no imputation of missing data will be performed. For the analysis of six month effectiveness, if the six month Raymond score or mRS values are missing and any earlier data are available, the most recent earlier value will be used.

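### The six-month endpoint labelled stable occlusion makes no reference to the end-of-procedure class, and the paired comparison promised elsewhere has no rule and no place in section 8

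*Combined protocol and SAP*

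**What the plan says.** Two definitions of stability stand in the current text.

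- **Six-month status.** The efficacy endpoint in section 3.1 (and in the Protocol Summary) is successful occlusion, "that is a stable IA occlusion, measured by Raymond Roy classification I or II taken at 6 months", with no re-treatment of the target aneurysm. Section 8.4 analyses the same thing: "stable IA occlusion, measured by Raymond Roy classification I or II without the need for re-treatment of the target IA", as a number and percentage with a 95% confidence interval.
- **Change between two angiograms.** The Statistical Analysis part of the Protocol Summary states: "Stability of occlusion will be evaluated by comparing the two angiographic studies that are 6 months apart". Section 7.3.1 says that the end-of-procedure and six-month angiograms "will be analyzed to determine Raymonds scale at both time points and stability of Raymond Roy score", and that the images go to the core lab.

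On missing six-month values, section 8.4 says: "If these endpoints are available at three months but not at six months, the three month values will be used for these analyses". The Protocol Summary has the same three-month rule for the Raymond score. Section 8.6 is wider: "if the six month Raymond score or mRS values are missing and any earlier data are available, the most recent earlier value will be used".

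**The concern.** Stability is a statement about change within a subject, and a second angiogram is needed to make it. The definition in 3.1 and 8.4 asks only where the subject stands at six months and whether the aneurysm was re-treated. A subject whose grade has worsened within the success range, and a subject who was not successfully occluded at the end of the procedure, both enter the numerator under the word stable.

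This is one of three listed efficacy endpoints. A reader of the final report would take the percentage as evidence of durability. Because no passage says which change in class counts as unstable, the meaning of the comparison promised in the Protocol Summary and in 7.3.1 would also have to be settled after the data are seen.

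**Working it through.** **1. The plan's own figure, for context.** Section 8.1 sizes the end-of-procedure endpoint with a performance goal of 69.7% (79.7% less 10 points), an assumed true rate of 82.6%, one-sided 0.025 and 80% power. By the normal approximation:

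n = [(1.960 × √(0.697 × 0.303) + 0.842 × √(0.826 × 0.174)) / (0.826 − 0.697)]² = 89.4, rounded up to 90.

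Power at 90 is 80.3%. The stated size reproduces, and nothing in it depends on the six-month definition.

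**2. All possible transitions.** The documents do not define the individual classes. I take three, ordered from I (best) to III (worst). Without re-treatment, the 8.4 rule gives:

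| End of procedure | I at six months | II at six months | III at six months |
|---|---|---|---|
| I | stable | stable | not stable |
| II | stable | stable | not stable |
| III | stable | stable | not stable |

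The three rows are identical, so the starting class plays no part. A re-treated aneurysm fails whatever its class.

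**3. Other readings of stable, also without re-treatment.**

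| Rule | Transitions counted | Number of 9 |
|---|---|---|
| Section 8.4: I or II at six months | I-I, I-II, II-I, II-II, III-I, III-II | 6 |
| I or II at six months and no worse than before | I-I, II-I, II-II, III-I, III-II | 5 |
| I or II at both times | I-I, I-II, II-I, II-II | 4 |
| I or II at both times and no worse | I-I, II-I, II-II | 3 |

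The disputed cells are I-II, III-I and III-II. The documents do not choose among the lower three rules.

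**4. Can the planned summaries recover the change?** No. Section 8.2 summarises occlusion at the end of the procedure and 8.4 summarises it at six months, each on its own. The Protocol Summary adds score distributions. If equal numbers of subjects move I to II and II to I, both distributions stay the same although individual grades have changed. Only a cross-tabulation shows this.

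**5. Missing six-month angiograms.** Under 8.6 the most recent earlier Raymond score may be the end-of-procedure one. A subject graded I or II after the procedure, with no follow-up angiogram and no recorded re-treatment, would then count as stable. In a paired comparison that subject's score would be compared with itself and show no change. Section 8.4 permits only the three-month value.

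**6. Size.** Let x be the share of subjects going I to II and y the share going III to I or II. On a common denominator, the 8.4 percentage exceeds the strictest rule by x + y, and exceeds the rule of I or II at both times by y. The documents give neither share. Purely as an illustration, assume x from 5% to 20%, y from 0% to 10%, and all 90 subjects with both angiograms:

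- against the strictest rule: from 90 × 0.05 = 4.5 to 90 × 0.30 = 27 subjects (5 to 30 points);
- against I or II at both times: from 0 to 90 × 0.10 = 9 subjects (0 to 10 points).

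The 90 is itself uncertain here. Section 6 ties it to complete 30-day status, not to six-month DSA.

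**The case against.** The case for leaving the text alone has several parts, and much of it stands.

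- **The rule is not the six-month class alone.** A reader might infer that it is. Both 3.1 and 8.4 also require no re-treatment, a condition that covers the whole interval. This stands, but it does not bring in the end-of-procedure class.
- **The comparison is planned.** A reader might infer that the study cannot answer its own stability question. The documents do not support that: DSA grading is scheduled at both times, images go to the core lab, and the Protocol Summary and 7.3.1 both commit to looking at stability. What is missing is narrower, namely a rule for the comparison and an analysis in section 8 that uses it.
- **I to II stays within the success range.** The primary endpoint uses the same cut-off, so remaining in I or II at both times is a coherent meaning of stable. A reader might infer that I to II must count as failure, or that it shows the neck reopening. No passage says so, and the classes are not defined. This stands, and it is why the change should be shown rather than classified by fiat.
- **II to I and III to III are not anomalies.** The strictest paired rule treats them exactly as 8.4 does.
- **The counting rule is printed beside the label.** True, but the same document gives the word a second meaning, and the label is what carries into a report.
- **The endpoint is descriptive.** True, and it limits the consequence.

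**Conclusion.** The point holds as an inconsistency between the label and the rule. As defined in 3.1 and 8.4, the six-month percentage measures adequate occlusion without re-treatment. It does not measure stability in the sense used in the Protocol Summary and 7.3.1. Six of nine transitions qualify, including one worsening (I to II) and two that start without successful occlusion (III to I, III to II). This follows from the wording and assumes only that the scale has three ordered classes.

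The numerical effect is unknown. A reader might take the 5 to 30 points in the illustration as an estimate of overstatement. It is not one, because it rests on assumed transition rates, a full 90 paired angiograms and the strictest of the possible rules. The primary hypothesis test, the performance goal and the sample size are untouched, and no safety conclusion depends on this endpoint. It should be corrected before the data are analysed, but it does not threaten the study's main result.

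**What to change.** 1. In 3.1, 8.4 and the matching Protocol Summary text, call the present endpoint 'adequate occlusion (Raymond Roy I or II) at six months without re-treatment'.
2. Add to 8.4 the paired comparison: a 3 x 3 table of end-of-procedure by six-month core-lab class in subjects with both DSA studies, with the number re-treated.
3. Base any percentage called stable on subjects with class I or II at the end of the procedure. Show I-to-II changes on a separate line, so that the result can be read with or without counting them as stable.
4. State that 8.6 may not supply an end-of-procedure score as the six-month value in this paired analysis. Reconcile 8.6 with 8.4 on which earlier Raymond score may be substituted at all. If the three-month substitution is kept, report how many subjects rest on it.

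The cost is protocol and SAP wording plus one cross-tabulation of grades already scheduled for collection. The stability percentage may be lower than the 8.4 figure. Its denominator will be smaller, because subjects without both angiograms and those at class III after the procedure drop out, so its confidence interval is likely to be wider.

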### **8.5 Subgroup Analysis**

Selected adverse event rates will be provided for subgroups including wide-necked ruptured versus unruptured intracranial aneurysms.

### **8.6 Missing Data**

Since the primary safety endpoint is defined immediately post-procedure and up to 30 days, the amount of missing data for this study is anticipated to be low and so no imputation of missing data will be performed. For the analysis of six month effectiveness, if the six month Raymond score or mRS values are missing and any earlier data are available, the most recent earlier value will be used.

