### **5.1.3 Subject Terminations**

Subjects will be considered discontinued from the study if any of the following occur:

1. Subject voluntarily withdraws from the study. Participation in the SUCCESS Study is voluntary. Subjects may withdraw consent at any time by completing an informed withdrawal form. Reasonable attempts will be made to determine the reason for withdrawal of consent. Data obtained prior to withdrawal enrolled will be included in endpoint data analysis, but no data will be obtained subsequent to withdrawal.
2. Investigator withdraws Subject from the study due to safety concerns. If, during the conduct of research, an Investigator determines that participation in the study may increase the hazard to a subject that is not acceptable, an Investigator may withdraw the Subject from the study due to safety concerns.
3. Lost to Follow Up: In the event that a Subject fails to return for the 30 days and/ or 6 months follow-up visits and is unable to be reached at the Subject's last known telephone number, a certified letter will be sent to the Subject's last known mailing address to remind the Subject of study obligations. Once all reasonable attempts to contact the Subject have been made, including contacting through the Subject's general practitioner, the Subject is considered lost to follow-up. Each attempt to contact a Subject will be documented.

If, during the conduct of the study, a Subject dies, all available information related to the event should be obtained. Within 24 hours from study staff becoming aware of the event, an appointed Rapid Medical representative/study monitor should be notified by completing the appropriate study termination forms in the Subject's eCRF.

Maximal completeness of the CRF for subject that died should be attempted and ensured by the following:

- If death occurs while the Subject is in the hospital, a copy of the death summary report should be submitted. In case of an autopsy, a copy of the autopsy report should also be submitted.
- If death occurs outside the hospital setting, effort should be made to obtain all information related to the death along with an Investigator's summary of the events associated with the death.

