### **7.2.3 Pre- Treatment Data:**

- Aneurysm size and location
- Pre-procedure mRS score (modified Rankin Scale)-up to 24h prior to treatment.
- Pre symptoms mRS
- NIHSS
- Pre op antiplatelet and/or coagulation medications

NIHSS will be performed by certified Study personnel.

mRS will be assessed by an independent clinician who is not a member of the investigational team.

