### **8.3 30-day post-procedure status**

30-day functional status will be assessed using the modified Rankin Scale (mRS). This scale runs from 0-6, from no symptoms to death as follows:

- 0 - No symptoms
- 1 - No significant disability. Able to carry out all usual activities, despite some symptoms.
- 2 - Slight disability. Able to look after own affairs without assistance, but unable to carry out all previous activities.
- 3 - Moderate disability. Requires some help, but able to walk unassisted.
- 4 - Moderately severe disability. Unable to attend to own bodily needs without assistance, and unable to walk unassisted.
- 5 - Severe disability. Requires constant nursing care and attention, bedridden, incontinent.
- 6 - Dead.

The frequency distribution and cumulative frequency distribution of the 30-day mRS will be summarized using counts and percentages.

All adverse events after discharge (device-related and non device-related) for each use of the Comaneci Embolization Assist Device will be summarized similarly to how periprocedural events will be summarized as described above. This includes counts, per subject incidence rate, exact binomial confidence intervals, and a separate set of adverse event listings that contain full descriptions of each adverse event including determination of the severity, seriousness, and relationship to the device or procedure.

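### The carry-forward rule for six-month mRS has no exception for death, does not exclude the pre-procedure score, and differs from section 8.4

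*Combined protocol and SAP*

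**What the plan says.** Section 3.1 lists the six-month clinical outcome among the efficacy endpoints: "Good clinical outcome- mRS shift @ 6 months (change @ 6 months from pre procedure) and tetrachotomized (0,1, 2, 3-6) mRS analysis". Three places say what to do when the six-month value is absent.

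- Section 8.6: "if the six month Raymond score or mRS values are missing and any earlier data are available, the most recent earlier value will be used".
- Protocol Summary, Statistical Analysis: "the last available earlier mRS values will be used if the six month value is not available".
- Section 8.4: "If these endpoints are available at three months but not at six months, the three month values will be used for these analyses".

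On death, section 8.3 introduces the mRS with the words "This scale runs from 0-6, from no symptoms to death as follows" and gives death the score 6. Section 5.1.3 sets out what sites do: "If, during the conduct of the study, a Subject dies, all available information related to the event should be obtained", and the sponsor is notified by "completing the appropriate study termination forms". It does not say that an mRS of 6 is to be entered for the visits that follow.

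On the baseline score, section 7.2.3 collects "Pre-procedure mRS score (modified Rankin Scale)-up to 24h prior to treatment", so an earlier mRS should exist for every treated subject.

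**The concern.** Carrying the last score forward is a weak but common choice for a living subject who misses a visit. It does not suit a subject who has died, because the outcome is known and is the worst on the scale. The written rule does not separate the two cases. A programmer who finds no six-month mRS record and follows section 8.6 would use the latest score recorded while the subject was alive.

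The rule also does not say how far back it may reach. If the only mRS on file is the pre-procedure one, carrying it forward makes the six-month shift zero by construction, and the subject counts as unchanged without any post-treatment observation.

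At stake is the reported six-month mRS distribution and shift in a study that enrols ruptured as well as unruptured aneurysms, so some deaths are foreseeable. Because sections 8.4 and 8.6 differ, two competent analysts could also produce different six-month tables from the same data.

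**Working it through.** **The plan's own figure, used here only for the denominator.** Section 8.1 gives 90 evaluable patients, from a performance goal of 0.697, an assumed rate of 0.826, one-sided 0.025 and 80% power. With the normal approximation:

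n = [(1.960 × √(0.697 × 0.303) + 0.842 × √(0.826 × 0.174)) / (0.826 − 0.697)]² = 89.4, rounded up to 90, with power 80.3% at 90.

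The figure reproduces. It concerns occlusion at the end of the procedure and does not involve mRS. The documents give no figure for mortality, for missing six-month mRS or for the six-month denominator, so 90 is an assumption below.

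**The three rules applied to the same subjects.**

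| Subject | Section 8.6 and synopsis, literal | Section 8.4, literal | Death read as an observed 6 |
|---|---|---|---|
| mRS 2 at day 30, dies on day 60, no later entry | 2 | no value | 6 |
| Dies before day 30, 6 entered at day 30 | 6 carried forward | no value | 6 |
| Alive, lost with only a pre-procedure mRS | pre-procedure score, shift 0 | no value | not applicable |

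The exposure is therefore mainly to deaths after the 30-day visit.

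**Can a subject have only a pre-procedure score?** Yes. Section 7.4 takes an mRS at 24 hours only if one is done, and Table 2 does not mark it there. The separate discharge visit in section 7.5 applies only when discharge falls outside the 24-hour window, which runs from 24 − 6 = 18 to 24 + 12 = 36 hours. A subject discharged inside that window may have no further mRS before day 30, even though section 3.1 lists mRS at discharge as a safety endpoint.

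**Size for deaths.** Assume d deaths, each last scored 0–2 and carried forward. The 3–6 category is then too low by d/90:

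- d = 1: 1.1 points
- d = 3: 3.3 points
- d = 5: 5.6 points
- d = 9: 10.0 points

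Example with 10 survivors at mRS 3–5 and 5 such deaths, with exact 95% intervals:

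- carried forward: 10/90 = 11.1% (5.5 to 19.5)
- death scored 6: 15/90 = 16.7% (9.6 to 26.0)

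If the last score was already 3–5, the category does not change. The shift still does: each death understates that subject's change by 6 minus the last score. If a mean shift were reported, one death would alter it by (6 − 0)/90 = 0.067 for a last score of 0, and by (6 − 4)/90 = 0.022 for a last score of 4.

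**Direction for living subjects.** Section 7.2.3 records the pre-procedure mRS separately from a pre-symptom mRS. In a ruptured case the pre-procedure score may already reflect the bleed, so carrying it forward could hide recovery as easily as decline.

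**The case against.** The strongest answer is that carry-forward acts only on absent values, and a known death is not absent. Section 8.3 gives death the score 6, and the six-month categories run up to 6, which would serve little purpose if deaths were never scored. Section 5.1.3 also asks that the case report form of a subject who dies be made as complete as possible. On that reading there is no bias. This stands as a reasonable interpretation, and it means a reader should not infer that the plan has settled on pre-death scores. It does not close the gap: no section says who enters the 6 or for which visits, and section 7.10 makes mRS an assessment by an independent clinician, which cannot take place after death.

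Four stronger readings are tempting but not supported.

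- **That a dead subject would be given a zero shift.** This needs a death with no post-procedure mRS and no 6 entered at any later time. Section 8.3 includes death in the 30-day scale, and section 8.4 gives no support for carrying the pre-procedure score.
- **That deaths before day 30 drop out of the 30-day distribution because section 8.6 rules out imputation.** Scoring a known death as 6 is not imputation.
- **That the error always favours the device.** That is true of deaths carried forward, but not shown for living subjects who are lost.
- **That deaths are hidden inside the 3–6 category.** Death is an adverse event of special interest in section 8.2 and is collected through 180 days, and the synopsis also plans to summarise the distribution of scores. A separate count of mRS 6 would be a display preference.

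**Conclusion.** The gap is real and of moderate weight. The carry-forward rule in section 8.6 and the synopsis does not exempt death or exclude the pre-procedure score, and it does not match section 8.4. Followed literally, it gives a favourable error for deaths after the 30-day visit that have no six-month entry: 1.1 points of the 3–6 category per death last scored 0–2, and an understated shift for any death carried at 0–5. For living subjects with only a baseline score, a zero shift is built in and its direction of error is unknown.

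These sizes rest on an assumed number of deaths, an assumed denominator of 90 and the literal reading of the rule. If deaths are entered as 6, the first error disappears. Section 8.4 treats the six-month mRS as descriptive, so the test of end-of-procedure occlusion, its power and the sample size of 90 are not touched.

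**What to change.** Before database lock, amend section 8.6 and the synopsis, and bring section 8.4 into line:

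1. A death on or before a scheduled time point is scored mRS 6 at that and every later time point, including 30 days and six months. This is done before any carry-forward and does not count as imputation.
2. Only post-procedure mRS values may be carried forward to six months. A subject with only a pre-procedure score is reported as missing.
3. Section 8.4, section 8.6 and the synopsis state one rule, including whether values other than the three-month one may be used.

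The cost is a few sentences and one derivation line. No new data are needed, since deaths and their dates are already collected. The six-month result may look slightly less favourable, and a few subjects will appear as missing rather than unchanged.

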### **6.1 Study Duration**

All patients who are treated with the Comaneci device and consented to allow data collection will be followed for 180 ( $\pm 21$ ) days post-procedure.

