## **7. Data Collection**

All procedures will be according to the standard practice at each site and determined by the treating physician including 6 months follow up. Procedures such as routine hospital examinations, brain CT scan or MRI will be performed according to each site's standard management protocol and relevant data will be properly documented in the patient's medical records.

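### The plan has no rule for six-month DSA or mRS values obtained after day 201, and the backward-only substitution in 8.6 can replace them with older results

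*Combined protocol and SAP*

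**What the plan says.** - **Endpoint.** Section 3.1 lists "Successful intracranial aneurysm (IA) occlusion, that is a stable IA occlusion, measured by Raymond Roy classification I or II taken at 6 months", with a tolerance of ± 21 days and the further condition that the target aneurysm needed no re-treatment. The clinical endpoint there is "Good clinical outcome- mRS shift @ 6 months (change @ 6 months from pre procedure"; no tolerance is attached to it.
- **Visit.** Sections 6.1 and 7.7 and Table 2 place the last visit, with both Raymond and mRS, at 180 ± 21 days. A three-month visit (90 ± 14 days) is recorded only where it is standard of care. Table 2 has no other post-procedure Raymond assessment.
- **Substitution.** Section 8.6 provides that "if the six month Raymond score or mRS values are missing and any earlier data are available, the most recent earlier value" is taken instead. Section 8.4 is narrower: "If these endpoints are available at three months but not at six months, the three month values will be used for these analyses". The synopsis names the three-month value for Raymond and the last earlier value for mRS.
- **Practice.** Section 7: "All procedures will be according to the standard practice at each site and determined by the treating physician including 6 months follow up". Section 7.8 has clinically indicated unscheduled assessments recorded in the eCRF but does not say whether they enter the analysis.

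**The concern.** The six-month occlusion endpoint asks whether the result at the end of the procedure lasted. If the DSA is done a little late, the study holds direct evidence on that question, yet the only written substitution looks backward. Where no three-month DSA was done, the value that 8.6 reaches is the end-of-procedure grade. The durability endpoint then repeats the primary endpoint for that subject. The synopsis's stability comparison, which needs two angiograms six months apart, would compare one angiogram with itself.

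The choice between using and setting aside a late value is also left open until the scans have been read. The 95% interval in 8.4 covers sampling error only and would not show the effect of either choice.

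**Working it through.** **1. Windows.** Six-month: 180 − 21 = day 159 to 180 + 21 = day 201. Three-month: 90 − 14 = day 76 to 90 + 14 = day 104.

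**2. The plan's own design figure.** Section 8.1 gives a performance goal of 69.7%, a hypothesised rate of 82.6%, one-sided alpha 0.025 and 80% power:

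n = [1.960·√(0.697·0.303) + 0.842·√(0.826·0.174)]² / (0.826 − 0.697)² = 89.4, rounded up to 90 (power 80.3% at n = 90).

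The figure reproduces. It concerns the end-of-procedure DSA only, so late follow-up cannot alter it.

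**3. One subject under each text.** Suppose Raymond I at end of procedure, no three-month DSA, Raymond III on a DSA at day 210, no re-treatment.

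| Reading | Value used | Six-month result |
|---|---|---|
| 3.1 window strict, then 8.6 | end-of-procedure grade I | success |
| 3.1 window strict, then 8.4 or synopsis | no substitute exists | missing |
| Day-210 DSA accepted as the six-month visit | grade III | failure |

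The same record gives three different answers, and the text does not choose between them. The rule is also lopsided: DSAs on day 150 and day 210 are each 9 days outside the window, but 8.6 can use the first and has no place for the second.

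**4. mRS.** Suppose mRS 3 at 30 days, no later value until mRS 1 on day 205. If day 205 is treated as out of window, 8.6 reports 3. Here the older value is the worse one.

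**5. Size, on assumptions.** The documents give neither a late share nor success rates for early against late values.

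Shift in six-month rate = (share late) × (success rate of carried values − success rate of late values).

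| Share late (of 90) | Carried | Late | Shift (points) |
|---|---|---|---|
| 10% (9) | 82.6% | 75% | 0.10 × 7.6 = +0.8 |
| 10% (9) | 82.6% | 65% | 0.10 × 17.6 = +1.8 |
| 20% (18) | 82.6% | 75% | 0.20 × 7.6 = +1.5 |
| 20% (18) | 82.6% | 65% | 0.20 × 17.6 = +3.5 |
| 10% or 20% | equal | equal | 0 |
| 10% (9) | 75% | 82.6% | 0.10 × (−7.6) = −0.8 |
| 20% (18) | 75% | 82.6% | 0.20 × (−7.6) = −1.5 |

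**6. Sign for Raymond when the end-of-procedure grade is carried.** Let *a* be the share of grades I/II that later become III, and *b* the share of grade III that later become I/II. At 82.6% initial success, shift = (share late) × (0.826*a* − 0.174*b*). It is upward unless *b* exceeds 0.826/0.174 ≈ 4.7 times *a*. The negative rows in step 5 need net improvement: starting from 75% with no loss at all, *b* must be 0.076/0.25 = 30%.

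**7. Scale.** At an illustrative 72/90 (80%), an exact 95% interval is 70.2% to 87.7%, a half-width of about 8.7 points. The shifts in step 5 are smaller than that.

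**The case against.** The strongest reply is that the plan never says late values are dropped. Section 8.6 acts on missing values and the synopsis on unavailable ones; a DSA on day 210 is neither in ordinary language. Section 8.4 repeats no window, and nothing excludes data obtained late. This stands: a reader might infer that the plan discards late results, but it only fails to give them a place. The gap remains, because 3.1 puts the window inside the Raymond endpoint definition and a strict analyst could follow 8.6 from there.

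Second, a reader might infer that late scans are bound to be common because Section 7 defers to site practice. The visit is nonetheless fixed at 180 ± 21 days, and 5.2.1 selects sites partly for their ability to supply the six-month angiogram. The late share is unknown.

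Third, a reader might infer that the error always flatters the device. For mRS, step 4 shows the reverse. For Raymond the argument is sound only where the end-of-procedure grade is carried, which 8.6 allows but 8.4 and the synopsis do not name. A known re-treatment would still count as failure, so only unre-treated recanalisation is hidden.

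Fourth, multiplying an assumed 30% late by an assumed 25% loss gives 7.5 points. That is a gross figure: it applies the loss to every late subject, allows no improvement and assumes that none had a three-month DSA. It should not be quoted as an estimate.

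**Conclusion.** The concern holds as a gap that should be closed, not as a stated rule that discards data. The Raymond window ends at day 201, substitution in 8.6 runs only backward, and no section says how a later assessment is used. Followed literally, an observed late DSA can give way to an older grade.

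- **Direction.** Probably toward success for Raymond when the end-of-procedure grade is carried; not fixed for mRS, where the window is also less firm because it comes only from the visit schedule.
- **Size.** Not derivable from the documents. About −1.5 to +3.5 points on the six-month rate, for 10–20% late and the success rates assumed above.
- **Reach.** The six-month results are descriptive. The primary effectiveness test and the sample size of 90 do not change.

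**What to change.** Amend 8.4 and 8.6 so that both set out one order of use:

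1. An observed DSA (or mRS) within 180 ± 21 days.
2. If there is none, the observed follow-up DSA (or mRS) after day 201, up to a limit the sponsor prespecifies; if there are several, the one nearest day 180.
3. Only then a carried earlier value, under a single rule. This requires reconciling 8.6 (any earlier value) with 8.4 (three-month value) and the synopsis (three-month value for Raymond), including whether the end-of-procedure grade may ever stand in for a six-month grade.

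State whether the ± 21 days applies to the mRS endpoint. Report how many values were out of window and how many were carried, and give the strict ± 21-day result as a sensitivity analysis.

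The cost is mainly wording, with one addition on data capture. Follow-up under 6.1 ends with the 180 ± 21 day visit, and 7.8 covers only clinically indicated assessments. The plan must therefore say that routine late DSA and mRS results are to be entered in the eCRF. No extra procedure is needed. The downside is a wider spread of assessment times, and some late scans may have been prompted by symptoms, which would over-represent poor results. The in-window sensitivity analysis shows the effect of both.
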